# 7.3.1 Safety Stopping Rules

The study treatment should be permanently discontinued if any of the following events occur:

- Severe drug-related diarrhea (increase of ≥ 7 stools per day).
- Any drug-related SAE.
- QTcF > 500 msec\*.
- Platelet count ≤ 50 x 10^9/L. To avoid laboratory errors and anomalous values, a
  platelet count ≤ 50 x 10^9/L must be confirmed with a repeated test performed on the
  next working day. Treatment should be stopped until the retest result becomes
  available. If the repeated platelet count is still ≤ 50 x 10^9/L, study treatment must be
  permanently discontinued. If the repeated test is acceptable, the patient can resume
  treatment.
- White blood cell count ≤ 2.0 x 10^9/L. To avoid laboratory errors and anomalous values, white blood cells ≤ 2.0 x 10^9/L must be confirmed with a repeated test performed on the next working day. Treatment should be stopped until the retest result becomes available. If the repeated white blood cells count is still ≤ 2.0 x 10^9/L, study treatment must be permanently discontinued. If the repeated test is acceptable, the patient can resume treatment.
- Hemoglobin ≤ 8.0 g/dL. To avoid laboratory errors and anomalous values, hemoglobin ≤ 8.0 g/dL must be confirmed with a repeated test performed on the next

17 June 2020 Page 48 of 110

working day. The treatment should be stopped until the retest result becomes available. If the repeated hemoglobin is still  $\leq 8.0$  g/dL, study treatment must be permanently discontinued. If the repeated test is acceptable, the patient can resume treatment.

The Investigator will follow up until resolution or acceptable stabilization of the event and document all the relevant information, as applicable. After the resolution/stabilization of the event, the patient will be withdrawn from the study and the EOS Visit (see Section 9.1.10) will be performed.

\* Based on average QTc value of triplicate ECGs. For example, if an ECG demonstrates a prolonged QT interval, 2 more ECGs should be obtained over a brief period, and then the averaged QTcF values of the 3 ECGs should be used to determine whether the patient should be discontinued from the study. If the mean QTcF value of the 3 replicates still meets the stopping criteria, the patient has to interrupt the study treatment, the medical monitor has to be informed and the value must be confirmed by central reading before withdrawing the patient from the study. The QTc has to be calculated with the Fridericia formula QTc = QT/RR1/3.

The Study treatment should be temporarily interrupted if any of the following events occur:

- Moderate or severe diarrhea (increase more than 4 stools per day).
- Platelet count < 75 x 10^9/L but > 50 x 10^9/L (treatment should be temporarily stopped, and the platelet count repeated within 1 week and retested until platelets are normal).
- White blood cell < 3.0 x 10^9/L but > 2.0 x 10^9/L (treatment should be temporarily stopped, and white blood cells re-measured within 1 week and retested until white blood cells are normal).
- Hemoglobin < 10.0 g/dL but > 8.0 g/dL (treatment should be temporarily stopped, and hemoglobin re-measured within 1 week and retested until hemoglobin is normal).
- Triglycerides > 300mg/dL (see also section 8.8)

The study treatment can be reduced by 20% of the current dose at which the AE leading to temporary interruption occurred, once platelets and/or white blood cell and/or hemoglobin and/or triglycerides are normalized, or diarrhea is mild. See Section 8.2.2 for more details.

The patient may have unscheduled visits if needed until the AE resolves, and will then continue the study as per scheduled visits. Further procedures (blood sample collection) may also be performed by a qualified trained nurse at the patient's home.

17 June 2020 Page 49 of 110

In addition, if a patient has a consistent (at least two consecutive evaluations) platelet count  $\leq$  150 x 10^9/L that does not meet stopping criteria for platelets, the Investigator will have to reduce the dose by 20% of the current dose. See Section 8.2.2 for more details.

Hematology parameters will be evaluated every 2 weeks during the first 2 months of treatment (Visits 4-7) to closely monitor these safety parameters.

Any decision concerning dose adjustment and/or modification of schedule of assessments can be discussed with the Medical Monitor, but the final decision remains with the Investigator only or authorized designee.

If a patient has a medical event not necessarily drug related that requires interruption of study treatment dosing for > 4 weeks, the Investigator can discuss the case with the medical monitor to decide whether the patient may resume study treatment, however the final decision remains with the Investigator only or authorized designee.

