### 9 STUDY PROCEDURES

Table 5 outlines the timing of procedures and assessments to be performed throughout the study. See Section 9.1 for additional details of study procedures.

17 June 2020 Page 59 of 110

Table 5: Schedule of Assessments

Month	-1 -4		0	1		2		3	6	9	12	13
Week			0	2 4		6	8	12	24	36	48	52
Visit window	+ 2 weeks		0	± 3 days	± 3 days	±3 days	± 3 days	± 7 days	± 7 days	± 7 days	± 7 days	± 7 days
	Vl	V2	V3	V4	V5	V6	V7	V8	V9	V10	V11	V12
Visit*	Screening		Rand								EOS/Early Withdrawal 	FUV 
Informed consent	X											
Eligibility criteria	X											
Medical history and demographic data	X											
Prior and concomitant medications	Х		X	Х	X		X	X	X	X	Х	x
Physical examination	X		X	X	X		X	X	X	X	X	X
Vital Signs	X		X	X	X		X	X	X	X	X	X
Weight	X		X	X	X		X	X	X	X	X	
Height	X										X	
ECG Test 	X		X	X	X		X	X	X	X	X	X
ЕСНО	X										X	
Pulmonary function tests 	X										X	
Serology 	X											
Hematology 	X		X	X	X	X	X	X	X	X	X	X
Blood chemistry 	X						X	X	X	X	X	X
Thyroid function tests (TSH, fT3, fT4)	X				x		x	x	X	X	X	x
Coagulation tests (PT and aPTT)	X						X	X	X	X	X	X
Urine analysis 	X						X	X	X	X	X	X
SF-36	X		1								X	
Time function tests (time to climb 4 standard steps, time to rise from floor, time to walk 10 m)	х							х	х	х	x	

17 June 2020 Page 60 of 110

Month	-1		0	1		2		3	6	9	12	13
Week	-4		0	2	4	6	8	12	24	36	48	52
Visit window	+ 2 weeks		0	± 3 days	± 3 days	±3 days	± 3 days	± 7 days	±7 days	± 7 days	± 7 days	± 7 days
	Vl	V2	V3	V4	V5	V6	V7	V8	V9	V10	V11	V12
Visit*	Screening		Rand								EOS/Early Withdrawal 	FUV 
6MWT	X		X					X	X	X	X	
MFM	X							X	X	X	X	
Muscle strength 	X							X	X	X	X	
PK blood sample collection 					X			X	X		X	
Biomarkers blood collection 			X						X		X	
Study treatment dispensation and accountability			Х					X	X	X		
Patient diary dispensation			X									
Patient compliance through diary								X	X	X	X	
AE assessment	X	X	X	X	X	X	X	X	X	X	X	X
MR + Muscular biopsy		$X^{11}$									$X^{13}$	

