- Serum blood chemistry: total bilirubin, direct bilirubin, alkaline phosphatase, amylase, ALT, AST, LDH, cystatin C, CRP, GGT, creatine kinase, total
  protein, albumin, uric acid, triglycerides, phosphorus, total cholesterol, LDL, HDL, sodium, potassium, chloride, calcium, glucose, creatinine, BUN,
  bicarbonate), NT-proBNP.
- Urinalysis: appearance, pH, specific gravity, protein, glucose, ketone bodies, blood and WBCs, and urobilinogen.
- Muscle strength tests: knee extension, elbow flexion by HHM.
- 10. Pharmacokinetic sample collection: sampling (2 pre-dose during the treatment and 4 post-dose) will be collected as described in the protocol during the following visits: 5 (4 weeks), 8 (12 weeks), 9 (24 weeks), and 11 (Week 48). At these visits, the patient will be asked to take the morning dose at site.
- 11. The first MRI (by Dixon technique), MRS tests and muscular biopsy have to be performed when all inclusion/exclusion criteria have been already evaluated and the patient is eligible. MRI/MRS and muscular biopsy can be performed in different days.
- 12 LTBP4 and osteopontin genotype after randomization and blood sample collection for serum circulating proteins (by an ELISA based system) at randomization, 6 months and at the end of treatment.
- 13 MRI/MRS and biopsy may be performed on different days. Treatment is to continue up to the last assessment.

17 June 2020 Page 62 of 110

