### 9.1.3 Visit 4 (Week 2 ± 3 days)

The following assessments will be performed at Visit 4, after 2 weeks (± 3 days) of treatment:

17 June 2020 Page 64 of 110

- Concomitant medications
- Physical examination
- Vital signs (blood pressure, heart rate and body temperature)
- Weight
- 12-lead ECG
- Blood collection for hematology
- AEs assessments

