## 9.1.4 Visits 5 (Week $4 \pm 3$ days)

The following assessments will be performed at Visit 5, after 4 weeks (± 3 days) of treatment. Patients will be instructed to take the morning dose at the site in case of pre-dose PK analysis.

- Concomitant medications
- Physical examination
- Vital signs (blood pressure, heart rate and body temperature)
- Weight
- 12-lead ECG
- Blood collection for hematology, thyroid function tests (TSH, fT3, fT4) and PK analysis

AEs assessments

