### 9.1.5 Visit 6 (Week 6 ± 3 days)

Visit 6 is required if the platelet values at any visit during the first month of treatment decreased more than 10% from the PLT value measured at the Randomization Visit (i.e. Visit 3-week 0) or at the discretion of the Investigator.

Visits 6 will be performed 6 weeks after the Randomization Visit (± 3 days) essentially for safety purposes, and the following assessments will be performed:

- Blood collection for hematology
- AE assessments.

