### 9.1.6 Visit 7 (Week $8 \pm 3$ days)

At Visit 7, after 2 months of treatment (± 3 days), the assessments listed below will be performed.

- Concomitant medications
- Physical examination
- Vital signs (blood pressure, heart rate and body temperature)

17 June 2020 Page 65 of 110

- Weight
- 12-lead ECG
- Blood collection for:
  - hematology
  - blood chemistry
  - coagulation tests (prothrombin time [PT] and activated partial thromboplastin time [aPTT])
  - thyroid function tests (TSH, fT3, fT4)
- Urine analysis
- AE assessments

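### The triglyceride interruption rule has no scheduled on-drug test behind it until week 8; the existing week 4 draw could supply one

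*Protocol*

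**What the plan says.** Protocol section 7.3.1 puts "Triglycerides > 300mg/dL (see also section 8.8") in the list of reasons for temporary interruption, beside the platelet, white cell, hemoglobin and diarrhea criteria. Under sections 7.3.1 and 8.2.2, treatment can be resumed 20% below the dose at which the event occurred, once the value is normal.

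The only scheduled panel that contains triglycerides is serum chemistry. Footnote 7 to Table 5 lists "albumin, uric acid, triglycerides, phosphorus, total cholesterol" among its analytes. The Table 5 row "Blood chemistry 7" is marked at V1, V7, V8, V9, V10, V11 and V12, and is blank from V3 to V6.

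The visit lists agree with the table:
- V3 (section 9.1.2) draws blood for hematology and biomarkers, before the first dose.
- V4 (section 9.1.3): "Blood collection for hematology".
- V5 (section 9.1.4): "Blood collection for hematology, thyroid function tests (TSH, fT3, fT4) and PK analysis".
- V6 (section 9.1.5) draws hematology only and is conditional: "Visit 6 is required if the platelet values at any visit during the first month of treatment decreased more than 10" per cent from the V3 value, or if the investigator wants it.
- V7 (section 9.1.6) is the first on-drug visit with chemistry: "after 2 months of treatment (± 3 days), the assessments listed below will be performed".

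Extra bloods are allowed but not scheduled. Section 12 lets study clinicians ask for additional blood tests, taken at the patient's home, and section 9.1.12 covers unscheduled visits. Section 7.3.1 says that "modification of schedule of assessments can be discussed with the Medical Monitor", with the final decision left to the investigator.

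**The concern.** A stopping rule works only as often as its trigger is measured. The platelet, white cell and hemoglobin rules in the same list have scheduled tests at V4 and V5, and at V6 when that visit is held. The triglyceride rule has none in that period. A patient without symptoms who passes 300 mg/dL in the first 8 weeks stays on full dose unless someone decides to look.

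The sponsor added the rule itself. Amendment 2 reports marked triglyceride rises in four treated patients, two of whom already had raised levels at baseline, and says the link with givinostat was still being studied. The amendment increased blood monitoring only through discretionary tests.

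Exclusion criterion 17 narrows the gap but does not close it, because it admits patients up to 1.5 times the upper limit of normal. The documents do not give that limit. If it is assumed to lie between 150 and 200 mg/dL, the entry ceiling is 1.5 × 150 = 225 to 1.5 × 200 = 300 mg/dL, so some eligible patients could start near the interruption threshold.

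What is at stake is how soon a laboratory abnormality is detected. The efficacy result is not at stake.

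**Working it through.** No sample size or test statistic is involved; the check is schedule arithmetic. Inputs are the visit days and windows in Table 5, counted from first dose at week 0: V4 14 ± 3, V5 28 ± 3, V7 56 ± 3, V8 84 ± 7, V9 168 ± 7, V10 252 ± 7 and V11 336 ± 7 days.

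**Scheduled on-drug tests before V7.** Triglycerides: 0. Hematology: 2 (V4, V5), or 3 when V6 is held. From V7 to V11 there are 5 chemistry tests.

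**Intervals between scheduled triglyceride tests.** The nominal interval is the difference between visit days. The range subtracts and adds both windows.

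| Interval | Plan as written | With V5 added |
|---|---|---|
| First dose to first test | 56 days (53 to 59) | 28 days (25 to 31) |
| V5 to V7 | no V5 test | 56 − 28 = 28 days (22 to 34) |
| V7 to V8 | 84 − 56 = 28 days (18 to 38) | unchanged |
| V8 to V9, V9 to V10, V10 to V11 | 84 days each (70 to 98) | unchanged |

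The 34 is a late V7 after an early V5: 59 − 25 = 34. The longest scheduled untested stretch in the first 8 weeks therefore falls from at most 59 days to at most 34.

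**Size of the reduction.** Counted from first dose, 28/56 = 0.50, with a range of 25/59 = 0.42 to 31/53 = 0.58. At two doses a day, 56 × 2 = 112 doses precede the first scheduled test now, against 28 × 2 = 56 with V5 added. Counted from the screening value at week −4, the untested interval falls from 4 + 8 = 12 weeks to 4 + 4 = 8, a cut of one third. With screening at week −6 it falls from 14 weeks to 10.

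**Adding V4 as well.** The first value would come at day 11 to 17, but the V5 to V7 interval would still be up to 34 days. V5 gives most of the gain.

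**Reach.** The current protocol is dated 17 June 2020. A patient still short of a nominal V5 on that date was randomised after about 20 May 2020 (17 June minus 28 days), or 17 May if V5 falls at the end of its window (minus 31 days). On the SAP date of 25 June 2020 the nominal cut-off is 28 May. SAP section 3.5 says that enrollment was finished and baseline data were in for all patients. SAP section 6.6 cites a version 1.0 report of the analysis of those data. Randomisation dates are not given, so a count of zero is likely but not proven.

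**The case against.** Five points can be made against acting on this.

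1. **Discretionary testing already covers it.** Amendment 2 responded to the signal with a new exclusion, the interruption rule, permission to treat raised levels and extra bloods when clinicians want them. It also lowered the starting dose, for platelet reasons. This stands in part. A reader might infer that the rule cannot operate before week 8, and the documents do not support that. They support only that nothing obliges anyone to test a patient without symptoms before then.

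2. **No early risk is shown.** A reader might infer that early rises are being missed. The documents do not say when the four rises occurred and give no early time course for triglycerides. Platelets differ: section 4.2.2 puts their low point at 2 to 3 weeks, which justifies two-weekly counts. The comparison with hematology therefore shows a difference in scheduling, not an equal hazard. This objection stands and limits the benefit that can be claimed.

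3. **The later gaps are longer.** From V8 on, chemistry is 12 weeks apart, up to 98 days. This is true, and a V5 test does nothing for it. The case for V5 is only that blood is already being drawn there.

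4. **Sample conditions.** Dosing is in a fed state, V5 pharmacokinetic samples may be pre-dose or up to 10 hours after the dose, and no fasting rule is stated. Assuming that food raises the value, a fed sample could trigger an interruption and a 20% dose cut. This stands, and a bare instruction to add the analyte would be incomplete. The existing chemistry visits share the problem.

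5. **The change may come too late.** Enrollment appears complete. This also stands, and it is the main reason to rate the point low.

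**Conclusion.** The gap is real, and Table 5 and the visit lists agree on it: no scheduled on-drug triglyceride value until day 53 to 59, with earlier detection left to choice. A V5 test would bring the first scheduled value to day 25 to 31 and the longest untested stretch in the first 8 weeks down to at most 34 days. Those figures rest on the Table 5 windows and on V3 being the day of first dose.

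This is a minor, inexpensive safety improvement, worth considering. The documents do not support reading it as evidence of harm, of an unmonitored trial, or of any threat to the primary analysis. Expected cases are fewer after the lower starting dose and criterion 17, and the number of patients still able to benefit is probably very small or zero.

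**What to change.** In Table 5 and section 9.1.4, add triglycerides to the V5 (week 4) draw and record whether the sample was fasting. State that a non-fasting value above 300 mg/dL is to be confirmed by a fasting repeat before the dose is reduced. Section 7.3.1 already requires a repeat before permanent discontinuation for platelets, white cells and hemoglobin, so a confirmatory test is familiar in this protocol. A V4 test is optional. A V3 test is not needed, since it is pre-dose and would only refresh the baseline.

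First check whether any patient has yet to reach V5. If so, the investigator can order the week 4 test now under sections 7.3.1 and 12, without waiting for an amendment. If the schedule change is classed as substantial, section 14.6.1 requires authority authorisation and a favourable ethics opinion first, which would shorten the remaining reach further.

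Cost: a small laboratory charge, a slightly larger V5 draw and an occasional repeat test. No new visit is needed, and V8, V9 and V11 already combine chemistry with pharmacokinetic sampling. A V4 test might need an extra tube, as only hematology is drawn there.

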### 8 TREATMENTS

# 8.1 Details of Study Treatments

The investigational study drug to be used in this study is givinostat (ITF2357) and a placebo. For the duration of the study, givinostat and placebo will be supplied by Italfarmaco S.p.A.

The characteristics of the study treatment are listed in the Table below:

17 June 2020 Page 50 of 110

Investigational Medicinal Drug Test treatment Comparator Product name: ITF2357/givinostat\* Placebo Dosage form: Oral suspension Oral suspension Bottle containing 140 mL of placebo, a Unit dose Bottle containing 140 mL of combination of 0.1% w/v Titanium strength: givinostat 10 mg/mL (opacifier, to resemble suspension appearance) and 0.1% w/v of an additional flavoring agent (to resemble the slightly bitterish aftertaste typical of the drug substance) Oral administration under fed Oral administration under fed Route of Administration conditions conditions See Table 3: Givinostat-Placebo See Table 3: Givinostat-Dosing instructions: Placebo Starting Dose Starting Dose. White to off-white or faintly White to off-white or faintly pink, Physical pink, homogenous suspension homogenous suspension when mixed description: when mixed Device included Two graduated dosing Two graduated dosing syringes for in the syringes for oral use: oral use: One 5 mL syringe and packaging: One 5 mL syringe and One 1 mL syringe One 1 mL syringe

Table 2: Investigational Medicinal Products

## 8.2 Dosage

### 8.2.1 Rational for Dose Selection

The dose for this study has been selected based on the dose ranging evaluation performed in the mdx mouse model, the results of the Phase 2 study in pediatric patients with Duchenne Muscular Dystrophy (DMD) (DSC/11/2357/43), and the evaluation of PK and efficacy results obtained in other inflammatory diseases.

The PK/PD analysis done with the data collected during the non-clinical studies in the mdx model showed that a blood AUC0-24 of at least 300 ng\*h/mL was estimated to be needed to exert the beneficial histological and functional effects in mice and thus was considered the target exposure for the exploratory Phase 2 study in the DMD population.

Study DSC/11/2357/43 was designed to first verify that doses of givinostat leading to an AUC0-24 of at least 300 ng\*h/mL in most DMD patients were tolerated and then to verify that

17 June 2020 Page 51 of 110

\*Givinostat is used to indicate the whole study drug name givinostat hydrochloride monohydrate. The dosages/concentrations of the study drug are expressed as givinostat hydrochloride monohydrate.

such exposures would translate into a significant histological benefit. Results confirmed that doses of 25/37.5 mg bid are tolerated, result in an AUC0-24 of at least 300 ng\*h/mL in the majority of treated DMD patients and lead to a significant histological benefit. In study DSC/11/2357/43, the effects of givinostat on the Muscle Fiber Area Fraction (primary endpoint of the study) and on the other key histological parameters (Total Fibrosis, Total Necrosis, Fatty Replacement) were comparable when patients who maintained the 37.5 mg b.i.d. dose throughout the study (n=7) were compared to those who reduced the dose to 25mg b.i.d. (n=12). In a post-hoc analysis, the Cross Sectional Area (CSA) of the muscle fibers in patients who maintained the 37.5mg b.i.d. dose throughout the study (n=7) was larger than that in patients who reduced the dose to 25mg b.i.d. (n=12); however a highly significant increase in CSA was seen in both dose groups.

On the other hand, clinical experience in chronic inflammatory diseases in adult and pediatric populations (i.e., Crohn's Disease, Psoriasis, Systemic Onset Juvenile Idiopathic Arthritis and Polyarticular Course Juvenile Idiopathic Arthritis) have shown that givinostat was overall not effective in controlling symptoms and biological features of these diseases at exposures (AUC0-24) comparable or lower to those obtained in study DSC/11/2357/43.

Based on these considerations, the Sponsor believes that doses leading to daily exposures lower than those obtained in study DSC/11/2357/43 are very unlikely to be effective and therefore chose an initial study dose to ensure a mean AUC0-24 similar to that achieved with 37.5 mg/bid during the DSC/11/2357/43 study in DMD patients (i.e., approximately 1150 ng\*h/mL).

Unfortunately, the majority of the patients treated with the starting dose used in protocol version 2.0 (i.e. dose leading to daily exposures obtained with 37.5 mg/bid in study DSC/11/2357/43) experienced a platelet count decrease that required dose reduction. Even if a strict regimen of platelet count monitoring and the implementation of a set of safety rules were adequate to ensure patient safety, these preliminary blinded results suggest that the starting dose indicated in protocol version 2.0 would be difficult to manage outside of a clinical trial environment. As a consequence, a new starting dose corresponding to the reduced dose of protocol version 2.0 (i.e. 26.7-46.7 mg b.i.d according to body weight) is proposed by the Sponsor in protocol version 3.0. This new starting dose ensures a mean

17 June 2020 Page 52 of 110

AUC0-24 similar to that achieved with 25 mg/bid during the DSC/11/2357/43 study in DMD patients (i.e., approximately 674 ng\*h/mL), which was safe and showed significant histological benefit.

Lastly, since weight was shown to significantly affect givinostat clearance, the initial dose will be adjusted to the body weight of the patient (see Section 8.2.2).

